7.1.7. Adverse Events of Special Interest

Events of interest will be identified by the use of either SMQs or MSTs. However, should additional cases not detected by the predefined search term listings be identified during the clinical review process, these cases will also be reported by respective category. Serious major adverse cardiovascular events (MACE) will not be adjudicated.

Adverse events of special interest include:

- All infections (defined as all PTs within the Infections and Infestations SOC)
- Serious infections (defined as all PTs within the Infections and Infestations SOC that are SAEs)
- Infections of special interest as defined below
 - A) Herpes zoster
 - B) Active tuberculosis
 - C) Opportunistic infections
 - D) Hepatitis B or C (HBV and HCV) infections
- Venous thrombotic events and pulmonary embolism
- Malignancies
- Gastrointestinal (GI) perforations
- Liver transaminase elevation
- Serious potential major adverse cardiovascular events (MACE) defined by the following terms:
 - A) Cardiovascular events
 - B) Myocardial infarction
 - C) Hospitalization for unstable angina
 - D) Transient ischemic attack
 - E) Stroke
 - F) Hospitalization for cardiac failure
 - G) Percutaneous coronary intervention

The number and percentage of patients with aforementioned events of special interest will be provided by the PT term.

A by-subject listing for all patients having AE of special interests at any time will be provided.

7.2. **Laboratory Evaluations**

Laboratory data collected during the study will be analyzed and summarized using both quantitative and qualitative methods. Summaries of laboratory data will be provided for the Safety Analysis Set and will include data collected up to the last dose of study drug plus 30 days for subjects who have permanently discontinued study drug, or all available data at the time of the database snapshot for subjects who were ongoing at the time of an interim analysis. The analysis will be based on values reported in conventional units. When values are below the LOQ, they will be listed as such, and the closest imputed value will be used for the purpose of calculating summary statistics as specified in Section 3.7. Hemolyzed test results will not be included in the analysis, but they will be listed in by-subject laboratory listings.

A baseline laboratory value for the placebo-controlled and entire study period will be defined as the last nonmissing measurement obtained on or prior to the date/time of first dose of any study drug. For the active treatment period, the baseline for the subjects originally randomized to placebo will be the measurement before or on the day when the first dose of active study treatment is administered.

A by-subject listing for laboratory test results will be provided by subject ID number and visit in chronological order for hematology, serum chemistry, and urinalysis separately. Values falling outside of the relevant reference range and/or having a severity grade of 1 or higher on the Common Terminology Criteria for Adverse Events (CTCAE severity grade) will be flagged in the data listings, as appropriate.

No formal statistical testing is planned.

7.2.1. **Summaries of Numeric Laboratory Results**

Descriptive statistics will be provided by treatment group for the following laboratory tests:

- Hematology
 - Hematocrit
 - Hemoglobin
 - Platelet count
 - Red blood cell count
 - White blood cell (WBC) count
 - Mean corpuscular volume

- Lymphocytes
- Monocytes
- Neutrophils
- Eosinophils
- Basophils
- Chemistry
 - Alanine aminotransferase (ALT)
 - Aspartate aminotransferase (AST)
 - Alkaline phosphatase (ALP)
 - Total bilirubin
 - Serum creatinine
 - Creatinine clearance by Cockcroft-Gault formula
 - Creatine phosphokinase (CPK)
 - Glucose
- Lipid Panel
 - Triglycerides
 - Total cholesterol
 - HDL
 - LDL
 - LDL/HDL ratio

Fasting results for lipid profile and serum glucose will be presented separately from overall results.

Change from baseline to a postbaseline visit will be defined as the visit value minus the baseline value. The mean, median, Q1, Q3, minimum, and maximum values will be displayed to the reported number of digits; SD values will be displayed to the reported number of digits plus 1.

Median (Q1, Q3) of the observed values for the laboratory tests specified above will be plotted using a line plot by treatment group and visit.

In the case of multiple values within the visit, data will be selected for analysis as described in Section 3.8.3.

7.2.2. **Graded Laboratory Values**

The CTCAE will be used to assign toxicity grades (0 to 4) to laboratory results for analysis. Grade 0 includes all values that do not meet the criteria for an abnormality of at least Grade 1. For laboratory tests with criteria for both increased and decreased levels, analyses for each direction (ie, increased, decreased) will be presented separately.

7.2.2.1. **Treatment-Emergent Laboratory Abnormalities**

Treatment-emergent laboratory abnormalities for the entire study period and in subjects discontinued treatment prematurely are defined as values that increase at least 1 toxicity grade from baseline at any postbaseline time point, up to and including the date of last dose of study drug plus 30 days for subjects who permanently discontinued study drug, or the last available date in the database snapshot for subjects who were still on treatment at the time of an interim analysis. If the relevant baseline laboratory value is missing, any abnormality of at least Grade 1 observed within the time frame specified above will be considered treatment emergent.

For the analyses of active treatment period, the baseline is the day of the first dose of active study drug administration.

For the analyses of placebo-controlled period, the lab abnormality occurring after (within 30 days) Week 12 visit is included only if subject did not continue treatment after Week 12.

The listing of all laboratory abnormalities will be provided.

7.2.2.2. **Treatment-Emergent Marked Laboratory Abnormalities**

Treatment-emergent marked laboratory abnormalities are defined as values that increase from baseline by at least 3 toxicity grades at any postbaseline time point, up to and including the date of the last dose of study drug plus 30 days for subjects who permanently discontinued study drug or the last available date in the database snapshot for subjects who were still on treatment at the time of an primary Week 12 analysis. If the relevant baseline laboratory value is missing, any Grade 3 or 4 values observed within the timeframe specified above will be considered treatment-emergent marked abnormalities.

Same rules as in the Section 7.2.2.1 apply for determination of TE abnormality in the placebo-controlled and entire study duration.

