GS-9876 is a highly selective SYK inhibitor with once daily dosing. Nonclinical studies show that SYK inhibition may have therapeutic value in the treatment of multiple autoimmune diseases such as RA, SLE, autoimmune cytopenias, as well as allergic and autoinflammatory diseases. Clinical experience with GS-9876 is limited.

In repeat dose toxicity studies of GS-9876 (in rats for up to 26 weeks and in cynomolgus monkeys for up to 39 weeks), the primary observed effects were reversible, dose-dependent decreases in circulating lymphocytes, and decreased lymphocytes in various tissues (spleen, lymph nodes, thymus, and/or bone marrow), consistent with the expected pharmacology of SYK inhibition {Barr 2012}. Additionally, effects on erythrocyte turnover were seen in rats, and effects on hemostasis (hemorrhage and thrombosis) were seen in monkeys. In clinical studies of GS-9876 in healthy volunteers, no safety signals were identified and no grade 3 or 4 AEs were reported. There were no clinically significant changes in vital signs, physical findings, laboratory parameters, or ECGs. Given the role of SYK in platelet activation and aggregation, bleeding time was evaluated in the study subjects; no clinically relevant prolongation was noted.

Filgotinib is contraindicated in pregnancy; highly effective contraception is to be used across all clinical studies to mitigate this risk.

Preclinical and clinical data support the further clinical development of filgotinib and GS-9876 due to their potential benefit as novel therapies in CLE, with an acceptable level of risk consistent with immunomodulation in this patient population. Controlled trials will be utilized to minimize risk to subjects, while gaining understanding of drug efficacy. The development of GS-9876 and filgotinib are expected to provide valuable alternatives to existing treatments for CLE and related diseases.

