6.4. Week 2 through Week 24 (Study Dosing Period)

The following assessments will be completed as specified in the Study Procedures Table (Appendix 2).

• Weight

- Symptom-driven physical examination
- Vital signs (blood pressure, heart rate, respiratory rate, and temperature)
- PGA
- CLASI
- Detailed target lesion assessment (see Section 6.9.2.3 for details)
- Photographs of areas with skin involvement (identifying subject features should be obscured, as much as possible)
- Detailed mucous membrane assessment (Weeks 2, 12, 14, and 24; see Section 6.9.2.4 for details)
- Subject questionnaires:
 - Subject's global assessment of CLE disease activity
 - Subject assessment of autoimmune disease-related dry eyes/mouth
 - Subject assessment of autoimmune disease-related body pain
 - Subject assessment of autoimmune disease-related joint pain/stiffness
 - Subject assessment of autoimmune disease-related fatigue
 - Subject assessment of CLE on sexual activity
 - SF-36
 - DLOI
 - TSQM
- Standard 12-lead ECG (Week 24 only)
- HCV monitoring (Weeks 12 and 24; if applicable)
- Obtain blood samples for:
 - Clinical Laboratory Tests (hematology, serum chemistry, and coagulation)
 - Fasting Lipids (Weeks 12 and 24; overnight fast [no food or drinks, except water] of at least 8 hours required prior to blood sample collection)
 - CRP and ESR
 - Quantitative Serum Immunoglobulin Test (Weeks 8 and 20)
 - Autoantibody Panel and Complement Levels (Weeks 12 and 24)

- Biomarker Samples (Weeks 2, 4, 12, and 24)
 - Whole Blood, Cytochex
 - o Whole Blood, Heparin
 - o Serum and plasma biomarker samples
 - vfPBMC sample
 - o PAXgene RNA sample
- Pharmacokinetic Samples (Week 2 [at least 30 minutes and up to 3 hours after dosing], Week 4 [anytime], Week 12 [within 2 hours prior to study drug administration], and Week 24 [within 2 hours prior to study drug administration])
- Obtain urine sample for:
 - Urinalysis
 - Urine pregnancy test (for females of childbearing potential)
 - Urine protein to creatinine ratio
- Re-randomization 1:1 upon completion of Week 12 assessments (subjects on placebo only, will be performed in a double-blind fashion via IWRS)
- Study drug dispensation (not applicable at Weeks 2 and 14 and not applicable at Week 24 for subjects who do not enter the 24-week extension period)
- Study drug accountability
- Review and record all adverse events and concomitant medications

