6.9.4. Clinical Laboratory Evaluations

The hematology, serum chemistry, and coagulation laboratory analyses will be performed at a central laboratory. Reference ranges will be supplied by the central laboratory and will be used by the investigator to assess the laboratory data for clinical significance and pathological changes.

Blood samples will be collected by venipuncture CCI in the arm at the time points indicated in the Study Procedures Table (Appendix 2). In addition, urine samples for the clinical laboratory assessments will be collected. An overnight fast (no food or drinks, except water) of at least 8 hours will be required prior to collection of blood samples for lipid testing.

• Refer to Appendix 6 for table of clinical laboratory tests.

Laboratory values outside the normal range will be flagged and clinical relevance will be assessed by the investigator (refer to Section 7.5). More frequent sampling as well as additional tests may be performed as deemed necessary by the investigator.

Note that in the case where clinically significant laboratory test results are a potential reason for discontinuation from the study drug and/or withdrawal from the study, retesting of the affected parameter(s) should be prompt (within 3 to 7 days) (see Section 3.5 for additional information).

The details of sample handling and shipment instructions will be provided in a separate laboratory manual.

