7.6.3. Grade 4 Laboratory Abnormality or Clinical Event

For Grade 4 laboratory abnormalities or clinical events not specified in Section 3.5, the following toxicity management guidelines apply:

- For a Grade 4 clinical event, or clinically significant (confirmed) laboratory abnormality, study drug should be permanently discontinued and the subject managed according to local clinical practice. The subject should be followed as clinically indicated until the laboratory abnormality returns to baseline or is otherwise explained, whichever occurs first. A clinically significant Grade 4 laboratory abnormality that is not confirmed by repeat testing should be managed according to the algorithm for the new toxicity grade.
- Study drug may be continued without dose interruption for a clinically non-significant Grade 4 laboratory abnormality (eg, Grade 4 creatine kinase after strenuous exercise or nonfasting triglyceride elevation that can be medically managed) or a clinical event considered unrelated to the study drug(s).

Grade 4 treatment-emergent toxicities should be noted by the investigator and brought to the attention of the Gilead Sciences Medical Monitor, who will discuss with the investigator and determine the appropriate course of action. All subjects experiencing AEs, regardless of if the AEs are treatment-related, must be monitored periodically until symptoms subside, any

abnormal laboratory values have resolved or returned to baseline levels or they are considered irreversible, or until there is a satisfactory explanation for the changes observed.

Histologic hemorrhage and thrombosis have been observed in cynomolgus monkeys that received GS-9876 at doses \geq 20 mg/kg/day. The clinical relevance of these findings to humans is unknown; these adverse events have not been reported in clinical studies of GS-9876. Any treatment-emergent adverse event involving significant bleeding or thrombosis is to be reported to the investigator and brought to the attention of the Gilead Sciences medical monitor or designee, to discuss the appropriate course of action.

Any questions regarding toxicity management should be directed to the Gilead Sciences Medical Monitor.

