7.2.2.3. Summaries of Laboratory Abnormalities

The following summaries (number and percentage of subjects) for treatment-emergent laboratory abnormalities will be provided by lab test and treatment group; subjects will be categorized according to the most severe postbaseline abnormality grade for a given lab test:

- Treatment-emergent laboratory abnormalities
- Treatment-emergent grade 3 or 4 laboratory abnormalities
- Treatment-emergent marked laboratory abnormalities

The summaries of treatment-emergent laboratory abnormalities will be presented by treatment group and highest grade for the placebo-controlled and active treatment period. The listing of all laboratory abnormalities will be provided.

For all summaries of laboratory abnormalities, the denominator is the number of subjects with nonmissing postbaseline values, with the baseline determined per Section 7.2.

By-subject listings of treatment-emergent Grade 3 or 4 laboratory abnormalities and marked laboratory abnormalities will be provided by subject ID number and visit in chronological order. This listing will include all test results that were collected throughout the study for the lab test of interest, with all applicable severity grades displayed.

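### The SAP plans no by-arm summary of PT, aPTT and INR values and no single count of subjects with any bleeding event, although bleeding is a named GS-9876 concern in the protocol

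*SAP*

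**What the plan says.** On the drug (GS-9876 in the protocol, lanraplenib in the SAP), Protocol 1.5 records that "effects on hemostasis (hemorrhage and thrombosis) were seen in monkeys". Protocol 7.6.3 repeats the finding, calls its relevance to humans unknown, and sets one rule for both halves of it: "Any treatment-emergent adverse event involving significant bleeding or thrombosis is to be reported to the investigator" and raised with the sponsor's medical monitor.

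On collection, Protocol 6.9.4 states: "The hematology, serum chemistry, and coagulation laboratory analyses will be performed at a central laboratory". Appendix 6 defines the coagulation panel as aPTT, PT and INR. Appendix 2 marks it in every visit column, including early termination and follow-up.

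On analysis, SAP 7.2.1 opens with "Descriptive statistics will be provided by treatment group for the following laboratory tests" and then names haematology, chemistry and lipid tests. SAP 7.2 gives the full by-subject results listing "in chronological order for hematology, serum chemistry, and urinalysis separately". In SAP 7.1.7 the relevant special-interest entries are "Venous thrombotic events and pulmonary embolism" and serious potential MACE. Coagulation appears in the SAP only in the schedule copied into its Appendix 1.

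**The concern.** Safety and tolerability are the trial's secondary objective. The protocol pairs bleeding with thrombosis for one of the two study drugs and samples coagulation throughout. The SAP carries the thrombosis half into its special-interest events and leaves the bleeding half out.

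Two outputs would therefore be missing if the SAP were followed as written. The first is a by-arm view of PT, aPTT and INR over time, which could show a modest shift that stays below a grading threshold. The second is a single number of subjects per arm with any bleeding event. Bleeding events can be coded to several preferred terms and organ classes. In arms of 20, 20 and 10, a few events could sit one per row. A grouping chosen after unblinding would be open to the charge that it was picked to suit the data.

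**Working it through.** No figure in the plan bears on this point. The plan's only computed design figure, 79% power for the primary endpoint, reproduces: with 10% drop-out the arms are 9 and 18, 2 / (2 × √(1/9 + 1/18)) = 2.449, and Φ(2.449 − 1.645) = 0.789. Nothing below depends on it.

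**Draws per subject (Protocol Appendix 2).**
- Through Week 24: screening and Day 1 (2), Weeks 2, 4, 8, 12, 14, 16, 20 and 24 (8), follow-up (1). Total 2 + 8 + 1 = 11.
- With the extension: add Weeks 30, 36, 42 and 48. Total 11 + 4 = 15.
- If all 50 subjects completed at least Week 24 and follow-up, the total would lie between 50 × 11 = 550 and 50 × 15 = 750 draws, each giving three results. Drop-out lowers this.

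**Where a coagulation result can appear in the SAP.**
- 7.2.1 numeric summaries and plots: no.
- 7.2 full by-subject results listing: no.
- 7.2.2 graded abnormalities: possibly, as far as the CTCAE scale grades these tests. The text is not restricted by panel, and it says "The listing of all laboratory abnormalities will be provided". The listing for Grade 3 or 4 and marked abnormalities also shows every result collected for the test concerned.
- What is left uncovered is descriptive statistics, change from baseline by arm, and a full listing that includes ungraded values.

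**Where a bleeding event can appear.**
- 7.1.6: yes, in the tables by SOC, HLT and PT and in the listing of all adverse events.
- 7.1.7: no category. A haemorrhagic stroke could fall under MACE. The provision for cases found on clinical review reports them under their own category, and bleeding has none. Counts in 7.1.7 are by preferred term.

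**Scale of a grouped count.** The documents give no bleeding rate, so the rates p below are assumptions. Expected subjects = n × p; P(≥1) = 1 − (1 − p)^20; P(≥2) = 1 − (1 − p)^20 − 20p(1 − p)^19.

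| Assumed rate | Expected in 20 | Expected in 10 | P(≥1 in 20) | P(≥2 in 20) |
|---|---|---|---|---|
| 2% | 0.4 | 0.2 | 33% | 6% |
| 5% | 1 | 0.5 | 64% | 26% |
| 10% | 2 | 1 | 88% | 61% |

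No cases in 20 would still leave a one-sided 95% upper bound of 1 − 0.05^(1/20) = 13.9%. A split of 2/20 against 0/10 gives a two-sided Fisher p of 380/870 + 90/870 = 0.54.

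**The case against.** The case against has four parts, and each limits what can be claimed.

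- **The signal is weak in people.** A reader might infer that haemostasis is the drug's main toxicology concern. Protocol 1.5 does not support that: it gives lymphocyte decreases as the primary effect. Protocol 1.3.2.2 places haemorrhage and thrombosis at 20 mg/kg/day and above in monkeys, and reports no haemostatic effect in the 39-week study, whose NOAEL of 15 mg/kg/day gives a 2.2-fold exposure margin at 30 mg. It also reports no change in platelets, PT, PTT, INR or bleeding time in two clinical studies. This stands. Those studies were in healthy volunteers (1.3.3), however, and the protocol keeps its escalation rule.
- **Some coagulation results will be shown.** A reader might infer that the report would hold no coagulation results by arm. SAP 7.2.2 does not support that, because graded abnormalities are tabulated by test and treatment group without limit to named panels. Threshold crossings are covered; values and trends are not.
- **Bleeding events are not lost.** A reader might infer that only a grouped category could reveal an imbalance. The general tables include the HLT level, every adverse event is listed, significant bleeding goes to the medical monitor, and a DMC and an internal unblinded team review safety. With about 50 subjects, a careful reader could assemble the count by hand. What is missing is a prespecified count. Even that would support no formal comparison, as the Fisher result shows.
- **The laboratory list is a selection.** A reader might infer a breach of the protocol. There is none: Protocol 8.6.3 promises summaries of selected tests only. Other collected tests, such as amylase, lipase and albumin, are also outside SAP 7.2.1. They belong to the chemistry panel, though, so they stay in the 7.2 by-subject listing. Of the three panels named in Protocol 6.9.4, coagulation alone has neither a numeric summary nor a full listing.

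**Conclusion.** The point holds as a gap in the SAP's safety outputs. As written, the plan gives no descriptive summary, no change over time by arm and no full listing for three coagulation tests drawn 11 to 15 times in a subject who completes 24 or 48 weeks and follow-up. It also gives no count of subjects with any bleeding event. It is modest in size: the data are collected, graded abnormalities and individual events remain visible, and no efficacy result or sample-size figure is affected. The conclusion rests on reading the lists in SAP 7.2, 7.2.1 and 7.1.7 as closed, which is how they are worded. The expected counts of 0.4 to 2 per active arm rest on assumed rates and show only that a grouped count would be descriptive.

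**What to change.** - SAP 7.2.1: add PT, aPTT and INR to the descriptive summaries, with change from baseline by visit and treatment group.
- SAP 7.2: add coagulation to the panels in the by-subject results listing.
- SAP 7.1.7: add a haemorrhage category defined by an SMQ or MST, as for the other categories. State explicitly that the number and percentage of subjects with any event will be given by treatment group, for the placebo-controlled period and the entire study. Without that sentence the section's reporting by preferred term would not yield the combined count. For data after Week 12, apply the exposure adjustment that SAP 7 already requires.

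The cost is a few table rows, one listing and one search definition. No new data, visits or subjects are needed. The change is best made before the SAP is finalised for the primary analysis, so that the grouping is fixed before unblinding; after that, the SAP's introduction requires it to be documented in the clinical study report.
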